## Subgroup Analysis

Safety, efficacy and immunogenicity endpoints may be analyzed in select subgroups specified below as applicable:

- Baseline SARS-CoV-2 Status (Positive, Negative)
- Pre-booster SARS-CoV-2 Status (Positive, Negative)
- Age ( $\geq 12$  and  $< 16$  Years,  $\geq 16$  and  $< 18$  Years)
- Sex (Female, Male)
- Race
- Ethnicity
- At Risk for Severe COVID-19 (Yes, No), as defined in SAP for Part 1A

## Analyses Approach

There are multiple parts in this study, all analyses and data summaries/displays will be provided by vaccination groups for each study part using appropriate analysis population unless otherwise specified.

All analyses will be conducted using SAS Version 9.4 or higher.

### 6.2. Background Characteristics

#### 6.2.1. Subject Disposition

The number and percentage of subjects in the following categories will be summarized by vaccination group as defined in [Section 6.1](#) based on specific analysis datasets for each part separately:

- Full Analysis Set
- Immunogenicity Subset

- Per-protocol (PP) Immunogenicity Subset
- Per-protocol (PP) Immunogenicity Subset - Pre-booster SARS-CoV-2 Negative (Part 1C-1 only)
- Per-protocol (PP) Immunogenicity Subset - Baseline SARS-CoV-2 Positive (Part 2 and Part 3)
- mITT1 Set (Long-term Analysis, Part 1C-1)
- Solicited Safety Set (except long-term analysis)
- Safety Set
  - When applicable, First Injection Safety Set and Second Injection Safety Set (Part 3 only)

The percentage will be based on subjects in that vaccination group within the Full Analysis Set for each part separately, except the Solicited Safety Set and Safety Set for which the percentages will be based on the vaccination group in the Safety Set (as treated) for each part separately.

For Part 1C-2, Part 2 and Part 3, the number of subjects in the following categories will be summarized based on subjects screened:

- Number of subjects screened
- Number and percentage of screen failure subjects and the reason for screen failure

The percentage of subjects who screen failed will be based on the number of subjects screened. The reason for screen failure will be based on the number of subjects who screen failed.

For long-term analysis, the number and percentage of subjects in each of the following disposition categories will be summarized by vaccination group based on the Randomization Set in Part 1A:

- Received first injection in Part 1A
- Received second injection in Part 1A
- Continuing and unblinded in open-label Part 1B
- Received cross-over first injection in Part 1B

- Received cross-over second injection in Part 1B
- Prematurely discontinued study vaccine during Part 1B and the reason for discontinuation
- Received booster dose in Part 1C-1
- Completed study
- Prematurely discontinued the study and the reason for discontinuation (for the entire study period, and for study parts in applicable subjects cohort)

For Part 1C-1 and Part 1C-2 analyses, the number and percentage of subjects in each of the following disposition categories will be summarized by vaccination group based on the Full Analysis Set for Part 1C-1 or Part 1C-2, respectively:

- Received booster dose
- Completed study
- Prematurely discontinued the study and the reason for discontinuation

For Part 2 and Part 3 analysis, the number and percentage of subjects in each of the following disposition categories will be summarized by vaccination group based on the Full Analysis Set for each part separately:

- Received each dose of IP
- Prematurely discontinued before receiving the second dose of IP and the reason for discontinuation
- Completed study
- Prematurely discontinued the study and the reason for discontinuation (for the entire study period, and for study parts in applicable subjects cohort)

A subject disposition listing will be provided, including informed consent, subjects who completed the study injection schedule (Long-term analysis, Part 2 and Part 3), subjects who completed study, subjects who discontinued from study vaccine (Long-term analysis, Part 2 and Part 3) or who discontinued from participation in the study, with reasons for discontinuation for each part separately. A separate listing will be provided for screen failure subjects with reasons for screen failure in Part 1C-2, Part 2 and Part 3.

A participant is considered to have completed the study if the participant has completed all periods of the study including the last visit or the last scheduled procedure, as shown in the SoA of each part.

### **6.2.2. Demographics**

Descriptive statistics will be calculated for the following continuous demographic and baseline characteristics: age (years), weight (kg, z-score), height (cm, z-score), and body mass index (BMI) (kg/m^2, z-score). Number and percentage of subjects will be provided for categorical variables such as gender, race, ethnicity. The summaries will be presented by vaccination group as defined in [Section 6.1 if applicable](#), based on the Safety Set, FAS, mITT1 Set, Immunogenicity Subset, and Per-protocol (PP) Immunogenicity Subset (by pre-booster SARS-CoV-2 status and overall for Part 1C-1 and Part 1C-2, by baseline SARS-CoV-2 status and overall for Part 2 and Part 3).

### **6.2.3. Medical History**

Medical history data will be coded by system organ class (SOC) and preferred term (PT) using the Medical Dictionary for Regulatory Activities (MedDRA).

The number and percentage of participants with any medical history will be summarized by SOC and PT based on the Safety Set. A participant will be counted only once for multiple events within each SOC and PT. SOC will be displayed in internationally agreed order. PT will be displayed in descending order of frequency and then alphabetically within SOC.

Medical history data will be presented in a listing.

Medical history data for participants who entered study in Part 1A will be provided in Part 1A analysis.

### **6.2.4. Prior and Concomitant Medications**

Prior and concomitant medications and non-study vaccination will be coded using the World Health Organization (WHO) drug dictionary (WHODD). The summary of concomitant medications will be based on the Safety Set. Categorization of prior, concomitant, and post medications is summarized in [Appendix C Table 4](#).

The number and percentage of subjects using concomitant medications and non-study vaccination during the 7-day follow-up period (i.e., on the day of injection and the 6 subsequent days) and during the 28-day follow-up period after each injection (i.e., on the

day of injection and the 27 subsequent days) will be summarized by vaccination groups as defined in [Section 6.1](#) as follows:

- Any concomitant medications and non-study vaccination within 7 Days Post Injection
- Any concomitant medications and non-study vaccination within 28 Days Post Injection
- Seasonal influenza vaccine within 28 Days Post Injection
- Antipyretic or analgesic medication within 28 Days Post Injection

A summary table of concomitant medications and non-study vaccination that continued or newly received at or after the first injection through 28 days after the booster injection will be provided by PT in descending frequency in the mRNA-1273 group (except in Part 3) or mRNA-1273.222 group in Part 3.

Medications taken to prevent pain or fever will be collected on eDiary and summaries will be provided based on the Solicited Safety Set by vaccination group as defined in [Section 6.1](#) for each injection (first or second or booster) in each Part (except Part 1B), including within 7 days after injection, beyond 7 days after injection.

Prior, concomitant and post medications and non-study vaccination will be presented in a listing.

#### **6.2.5. Study Exposure**

Study IP administration data will be presented in a listing for each Part separately.

Study duration will be summarized since the first injection, since the second injection in long-term analysis, in Part 2 and Part 3, and since booster injection in Part 1C-1, Part 1C-2.

#### **6.2.6. Major Protocol Deviations**

Major protocol deviations are a subset of protocol deviations that may significantly impact the completeness, accuracy, or reliability of the study data or that may significantly affect a subject's rights, safety, or well-being. Major protocol deviations rules will be developed and finalized before database lock.

The number and percentage of the subjects with each major protocol deviation type will be provided by vaccination group as defined in [Section 6.1](#) based on the Full Analysis Set (FAS).

Major protocol deviations will be presented in a listing.

### 6.3. Safety Analysis

Safety and reactogenicity will be assessed by clinical review of all relevant parameters including solicited ARs (local and systemic), unsolicited AEs, SAEs, MAAEs, AESI, AEs leading to withdrawal from study vaccine and/or study participation, vital signs, and physical examination findings. Unsolicited AEs will be coded by SOC and PT according to the MedDRA. The Toxicity Grading Scale for Healthy Adult and Adolescent Volunteers Enrolled in Preventative Vaccine Clinical Trials (DHHS 2007) is used in this study for solicited ARs as presented in [Table 6 from protocol](#).

All safety analyses will be based on the Safety Set, except summaries of solicited ARs which will be based on the Solicited Safety Set. All safety analyses will be provided by vaccination group unless otherwise specified.

#### 6.3.1. Adverse Events

A treatment-emergent AE (TEAE) is defined as any event occurring during the study not before exposure to study vaccine or any event already present that worsens after exposure to study vaccine. [Note: worsening of a pre-existing condition after vaccination will be reported as a new AE.]

Adverse events will also be evaluated by the investigator for the coexistence of MAAE which is defined as an AE that leads to an unscheduled visit to a healthcare practitioner.

Unsolicited AEs will be coded by PT and SOC using MedDRA and summarized by vaccination group, and stage (up to 28 days after any vaccination and overall stage [Long-term analysis, Part 2 primary series phase], up to 28 days after booster dose and overall stage [Part 1C-1, Part 1C-2], up to 28 days after each vaccination, after first injection and before second injection, after second injection, and throughout the study [Part 3]; see [Section 6.1](#) for definitions of vaccination group and stage).

All summary tables (except for the overall summary of AEs) for unsolicited AEs will be presented by SOC and PT for TEAEs with counts of subjects included. SOC will be displayed in internationally agreed order. PT will be displayed in descending order of frequency of mRNA-1273 (except Part 3) or mRNA-1273.222 group (Part 3) and then alphabetically within SOC. When summarizing the number and percentage of subjects with an event, subjects with multiple occurrences of the same AE or a continuing AE will be counted once. Subjects will be presented according to the highest severity (the strongest

relationship) in the summaries by severity (of related AEs), if subjects reported multiple events under the same SOC and/or PT.

Percentages will be based upon the number of subjects in the Safety Set for specified analysis within each vaccination group except summary after second injection in Part 3, which will be based on the Second Injection Safety Set.

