## **6.6. Long-term Analysis (including Part 1B)**

Long-term analysis will be performed including data collected in the Open-label Observational Phase (Part 1B), and prior to BD if a BD is received. The analysis will include participants who received mRNA-1273 in Part 1A and remained in the study with or without unblinding, and participants who received placebo in Part 1A and received mRNA-1273 in Part 1B after unblinding. Long-term analysis of applicable safety, efficacy, and immunogenicity endpoints will be summarized descriptively by treatment cohort without treatment group comparison.

In the long-term safety analysis, unsolicited AEs (SAE, AESI, MAAE, and AE leading to discontinuation) and deaths will be summarized.

In the long-term immunogenicity analysis, nAb and bAb values will be summarized at specified timepoints.

In the long-term efficacy analysis, the incidence rates of COVID-19 and of SARS-CoV-2 infection cases will be counted starting 14 days after the second dose of IP for participants in treatment cohorts of mRNA-1273 and Placebo, or starting 14 days after the second dose of mRNA-1273 for participants in the Placebo-mRNA-1273 Cohort. Incidence rate with 95% CI adjusting for person-time will be provided. The incidence rate of asymptomatic SARS-CoV-2 infection will also be provided.

Incidence rate will be analyzed by calendar month in the Long-term analysis.

Additional details for the Long-term analysis will be provided in a separate SAP (Part 1B, Part 1C, Part 2 and Part 3).

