## 9.6. Appendix F Schedule of Assessments (Part 1B, Open-label Observational Phase for Subjects Who Previously Received Placebo)

	Visit Number	7	8	9	10	11
	Type of Visit	C	C	C	SC 	C
Study Visit Day	(~D209/ Participant Decision Visit) OL-D1	OL-D29	OL-D57 	OL-D113	OL-D178 	
Window Allowance (Days)	-56/+56 	-3/+7	±14	±3	±14	
Days Since Most Recent Injection	0	28	28	84	84	149
Informed consent form	These assessments are already performed as part of the regular D209 Visit.		X			X
Blood for vaccine immunogenicity			X			
Nasopharyngeal or nasal swab sample for SARS-CoV- 2 			X			
Physical examination including vital signs 						X
Pregnancy testing						
Study injection (including 30-minute postdosing observation period)	X	X				
Informed consent for BD				X 		
Recording of MAAEs and concomitant medications relevant to or for the treatment of the MAAE 	X	X	X	X	X	X
Recording of SAEs and concomitant medications relevant to or for the treatment of the SAE 	X	X	X	X	X	X

	Visit Number	7	8	9	10	11
Type of Visit	C	C	C	SC 	C	
Study Visit Day	(~D209/ Participant Decision Visit) OL-D1	OL-D29	OL-D57 	OL-D113	OL-D178 	
Window Allowance (Days)	-56/+56 	-3/+7	±14	±3	±14	
Days Since Most Recent Injection	0	28	28	84	149	
Recording of AESI	X	X	X	X	X	
Recording of concomitant medications and nonstudy vaccinations 	X	X	X	X	X	
Surveillance for COVID-19/ Unscheduled visit	visit  /	X	X	X	X	
Study completion (for Part 1B)					X	

Abbreviations: AE = adverse event; AESI = adverse event of special interest; C = clinic visit; COVID-19 = coronavirus disease 2019; D = Day; M = month; MAAE = medically attended AE; NP = nasopharyngeal; OL = open-label; PCR = polymerase chain reaction; RT-PCR = reverse transcriptase polymerase chain reaction; SAE = serious adverse event; SARS-CoV-2 = Severe Acute Respiratory Syndrome coronavirus 2; SC = safety (telephone) call.

1. The Participant Decision Visit may be performed over multiple visits. Once the Participant Decision Visit has been initiated, all assessments must be completed within a 7-day period.
2. After the OL-D57 visit, Part 1B participants who choose to receive BD will have one additional safety call at OL-D113 prior to entering Part 1C-1..

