### **3. Study Endpoints**

#### **3.1. Part 1B, Open Label**

##### **3.1.1. Exploratory Endpoints**

The exploratory endpoints are the following:

- MAAEs through the last day of study participation or the booster dose if applicable
- SAEs through the last day of study participation or the booster dose if applicable
- AESIs through the last day of study participation or the booster dose if applicable
- AEs leading to discontinuation from study participation through the last day of study participation or the booster dose if applicable
- The incidence of SARS-CoV-2 infection (symptomatic or asymptomatic infection) counted starting 14 days after the second dose and after the first dose of mRNA-1273, including Part 1A and Part 1B for mRNA-1273 cohort, and Part 1B for placebo-mRNA-1273 cross-over cohort
- To evaluate the incidence of asymptomatic SARS-CoV-2 infection after vaccination with mRNA-1273 measured by RT-PCR and/or bAb levels against SARS-CoV-2 nucleocapsid protein (by Roche Elecsys) counted starting 14 days after the second dose and after the first dose of mRNA-1273 in participants with

negative SARS-CoV-2 at baseline, including Part 1A and Part 1B for mRNA-1273 cohort, and Part 1B for placebo-mRNA-1273 cross-over cohort

- The incidence of the first occurrence of symptomatic COVID-19 starting 14 days after the second dose and after the first dose of mRNA-1273, including Part 1A and Part 1B for mRNA-1273 cohort, and Part 1B for placebo-mRNA-1273 cross-over cohort

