**Treatment groups:**

The following vaccination groups will be used for summary purposes:

- Long-term Analysis (Part 1A plus Part 1B):
  - mRNA-1273: Participants from Part 1A mRNA-1273 group
  - Placebo - mRNA-1273: Participants from Part 1A placebo group who cross over and receive mRNA-1273 in Part 1B

- Part 1C-1 Homologous Booster Dose Analysis:
  - mRNA-1273 - Booster: Participants from Part 1A mRNA-1273 group who received booster dose in Part 1C-1
  - Placebo - mRNA-1273 - Booster: Participants from Part 1A placebo group who crossed over to receive mRNA-1273 in Part 1B, and received booster dose in Part 1C-1.
- Part 1C-2 Heterologous Booster Dose Analysis: Heterologous Booster
- Part 2: mRNA-1273 50 µg
- Part 3: mRNA-1273.222 50 µg

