### **6.3.1.1. Incidence of Adverse Events**

An overall summary of unsolicited TEAEs including the number and percentage of subjects who experience the following will be presented:

- Any unsolicited TEAEs
- Any serious TEAEs
- Any fatal TEAEs
- Any unsolicited medically-attended TEAEs
- Any unsolicited TEAEs leading to discontinuation from study vaccine
- Any unsolicited TEAEs leading to discontinuation from participation in the study
- Any unsolicited severe TEAEs
- Any AESI of MIS-C
- Any AESI other than MIS-C

The table will also include number and percentage of subjects with unsolicited TEAEs that are treatment-related in each of the above categories. Safety summary tables for Part 1C-1 will be provided separately from Part 1A and Part 1B.

In addition, listings containing individual subject adverse event data for unsolicited AEs, unsolicited TEAEs leading to discontinuation from study vaccine, unsolicited TEAEs leading to discontinuation from participation in the study, serious AEs, unsolicited medically-attended AEs, AESI of MIS-C and AESI other than MIS-C (including myocarditis and/or pericarditis) will be provided separately for placebo-mRNA-1273 group in Part 1B, and each group receiving the injection in Part 1C-1, Part 1C-2, Part 2 and Part 3. The safety data for the original mRNA-1273 group in open label will be included in Part 1A listings with a flag for open label phase.

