### **6.3.1.2. TEAEs by System Organ Class and Preferred Term**

The following summary tables of TEAEs will be provided by SOC and PT using frequency counts and percentages (i.e., number and percentage of subjects with an event):

- All unsolicited TEAEs
- All unsolicited TEAEs that are treatment-related
- All serious TEAEs
- All serious TEAEs that are treatment-related
- All unsolicited TEAEs leading to discontinuation from study vaccine
- All unsolicited TEAEs leading to discontinuation from participation in the study
- All unsolicited Severe TEAEs
- All unsolicited Severe TEAEs that are treatment-related
- All unsolicited medically-attended TEAEs
- All unsolicited medically-attended TEAEs that are treatment-related
- All AESI of MIS-C
- All AESI other than MIS-C

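### The long-term safety tables call for all unsolicited TEAEs, but the crossover schedule provides for recording only MAAEs, SAEs and AESIs, so those rows would understate events in the placebo-mRNA-1273 cohort

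*SAP*

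**What the plan says.** The submission contains two plans: the SAP for Part 1A, and a second SAP for Parts 1B, 1C, 2 and 3.

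**Second SAP, planned tables.** Section 6.3.1 summarises unsolicited AEs by vaccination group and stage, and gives the long-term analysis two stages: "up to 28 days after any vaccination and overall stage [Long-term analysis, Part 2 primary series phase". Section 6.3.1.1 adds a general overview table: "An overall summary of unsolicited TEAEs including the number and percentage of subjects who experience the following will be presented". Its rows include any unsolicited TEAE, severe unsolicited TEAEs and their treatment-related counterparts. Section 6.3.1.2 lists tables by SOC and PT, among them "All unsolicited TEAEs that are treatment-related". Neither section exempts the long-term analysis. Section 6.3.1.1 also plans listings, including one of unsolicited AEs, that "will be provided separately for placebo-mRNA-1273 group in Part 1B".

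**Second SAP, cohorts and endpoints.** Section 6.1 (Treatment groups) sets the original mRNA-1273 arm beside a second cohort: "Placebo - mRNA-1273: Participants from Part 1A placebo group who cross over and receive mRNA-1273 in Part 1B". The Part 1B endpoints in Section 3.1.1 are MAAEs, SAEs, AESIs and "AEs leading to discontinuation from study participation through the last day of study participation or the booster dose if applicable". There is no 28-day unsolicited-AE endpoint.

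**SAP for Part 1A.** Section 6.6 says that in the long-term safety analysis "unsolicited AEs (SAE, AESI, MAAE, and AE leading to discontinuation) and deaths will be summarized", and leaves additional details to the second SAP. In Appendix F (Part 1B, former placebo recipients) the event-recording rows are "Recording of MAAEs and concomitant medications relevant to or for the treatment of the MAAE", a matching row for SAEs, and a row for AESIs. Appendix E, which the original mRNA-1273 arm follows, has a row for recording unsolicited AEs.

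**The concern.** One table would carry two cohorts whose unsolicited AEs were ascertained differently, under one row label. Percentages use the Safety Set of each group as denominator, so a crossover participant with an unsolicited AE that nobody was scheduled to record counts as having had none. A reader of the any/all unsolicited rows, or of the SOC/PT tables beneath them, could not tell an event that did not occur from one that was not collected.

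At stake is the description of safety after two doses of vaccine in the former placebo recipients. The two SAPs also give different instructions for the same analysis, so a programmer following the second SAP and one following Section 6.6 of the first would produce different table sets.

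**Working it through.** The plan gives no event rate or other figure to reproduce here, so the check is a side-by-side reading followed by a small illustration on assumed values.

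**1. Which post-dose windows each cohort contributes.** The long-term analysis-period table (second SAP, Section 6.1) starts the safety period of both cohorts at the first dose of mRNA-1273. For the original arm that is the Part 1A dose; for the crossover arm it is the Part 1B dose.

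**2. What the schedules record in those windows.**

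| Event type | mRNA-1273 cohort, Part 1A doses (Appendix E) | Crossover cohort, Part 1B doses (Appendix F) |
|---|---|---|
| All unsolicited AEs | row present | no row |
| MAAEs | row present | row present |
| SAEs | row present | row present |
| AESIs | row present | row present |

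**3. Could the missing row be an artefact of text extraction?** Unlikely. Appendices E, G, H, I, J, K and L all keep an unsolicited-AE row. Two other places independently describe the restricted set: the Part 1B endpoints (second SAP, Section 3.1.1) and Section 6.6 of the SAP for Part 1A. Parts 1A, 1C-1, 1C-2, 2 and 3 each have a 28-day unsolicited-AE endpoint; Part 1B does not.

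**4. Does the second SAP exempt Part 1B elsewhere?** Yes. Section 5 makes the Solicited Safety Set inapplicable to Part 1B, and Section 6.3.2 excludes Part 1B from eDiary solicitation. Sections 6.3.1 to 6.3.1.2 make no such exception for unsolicited AEs.

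**5. Which rows are affected.** The any/all unsolicited rows are fully exposed, as is the Part 1B listing of unsolicited AEs. The severe and treatment-related rows are exposed only for events that are not also MAAEs, SAEs or AESIs. The MAAE, SAE and AESI rows rest on the same recording in both cohorts.

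**6. Illustration of size (assumed values, none from the documents).** Let p be the true 28-day risk of any unsolicited TEAE, equal in both cohorts and fully captured in Part 1A. Let f be the fraction of participants with such an event whose event is captured in Part 1B. The mRNA-1273 cohort shows p, the crossover cohort shows p × f, and the displayed ratio is (p × f)/p = f. With p = 20%:

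| f | Crossover shows | mRNA-1273 shows | Ratio |
|---|---|---|---|
| 0.25 | 20% × 0.25 = 5% | 20% | 0.25 |
| 0.50 | 20% × 0.50 = 10% | 20% | 0.50 |
| 0.75 | 20% × 0.75 = 15% | 20% | 0.75 |

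Because f cannot exceed 1, incomplete capture can only lower the crossover figure. The ratio simply returns whatever f is assumed, so the table shows the mechanism and is not an estimate.

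**The case against.** The strongest reply is that the limit is already written. Section 6.6 of the SAP for Part 1A restricts long-term safety, and the second SAP is meant to add details, not to revoke it. Sections 6.3.1 to 6.3.1.2 are a generic list serving several study parts, and Section 6.1 says the safety periods are used as applicable to each cohort. On that reading both cohorts would be tabulated on the same restricted categories. This reading is possible, but it does not remove the conflict: Section 6.3.1 names the long-term analysis explicitly, the table list has no exemption, and the unsolicited-AE listing is assigned by name to the crossover group.

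A second reply is that a missing schedule row does not prove non-collection. Appendix F also lacks a row for AEs leading to discontinuation, yet Section 3.1.1 makes these a Part 1B endpoint, and the full collection rules may be in the protocol, which is not shown. That stands as a caution: the documents establish that systematic recording is not scheduled, not that no other unsolicited AE will ever reach the database.

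A third reply concerns the severe and related rows. A severe event that prompts an unscheduled healthcare visit is an MAAE by definition, and Appendix F (footnote 4) sends clinically significant visit findings to the MAAE category. Many severe events would therefore be captured in both cohorts. This narrows the gap in those rows without closing it.

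A reader might infer that the crossover cohort will look safer across its whole safety profile, or that a particular fold difference can be predicted. The documents support neither. The categories that form the Part 1B endpoints and have rows in both schedules (MAAEs, SAEs and AESIs) are unaffected, and no capture fraction is given.

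**Conclusion.** The inconsistency is real and limited. Followed as written, Sections 6.3.1 to 6.3.1.2 of the second SAP would put a partly collected event set for the crossover cohort under the same label as a fully collected one for the mRNA-1273 cohort. The any/all unsolicited rows would be understated for the crossover cohort, and the severe and related rows to a lesser and unknown extent.

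The size cannot be derived from the documents. Under equal underlying risk and full capture in Part 1A, the displayed ratio equals the unknown fraction captured in Part 1B. The conclusion also assumes that Appendix F reflects actual collection in Part 1B.

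The harm is a misleading descriptive display, not a biased test. Section 6.6 plans no comparison between cohorts, Part 1B safety is exploratory, and no success criterion of the study changes. The point should still be corrected, because the error is in the output itself and costs little to avoid.

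**What to change.** - **Tables.** In Sections 6.3.1, 6.3.1.1 and 6.3.1.2 of the second SAP, restrict the long-term analysis to SAEs, MAAEs, AESIs, AEs leading to discontinuation and deaths, with a cross-reference to Section 6.6 of the SAP for Part 1A. Alternatively, show the any/all, severe and treatment-related unsolicited rows for the mRNA-1273 cohort only, and mark them as not systematically collected for the crossover cohort.
- **Listing.** Apply the same restriction to the Part 1B listing of unsolicited AEs in Section 6.3.1.1, or give it the same note.
- **Reconciliation.** Reconcile Appendix F with Section 3.1.1 on AEs leading to discontinuation, which are a Part 1B endpoint without a row in that schedule, and state where they are captured.

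The cost is SAP wording and fewer or footnoted tables. No new data, sample size or test is involved.
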